3.3 Study Population

Only subjects who completed a previous pegvaliase study will be enrolled into this study.

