4.1.2 Safety

The safety population will consist of all subjects who receive at least one dose of study drug throughout the study duration of any of the phase 2 studies (PAL-002, PAL-004, 165-205, PAL-003).

4.1.3 PK

The PK population will consist of all subjects who receive any amount of study drug and have post-treatment plasma pegvaliase concentration measurements in any of the phase 2 studies (PAL-002, PAL-004, 165-205, PAL-003).

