4.6 Handling of Dropouts and Missing Data

Subjects who discontinued prematurely will not be replaced. To investigate the primary objective, last observation carry forward (LOCF) imputation approach will be used as sensitivity analyses.

	SAP PAL-003 Amendment 1 version 1.0	Page 13
---	-------------------------------------	---------

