11 EXTENT OF EXPOSURE TO STUDY DRUG

Exposure will be summarized using descriptive statistics such as n, mean, standard deviation, median, minimum, and maximum for the following variables:

- Average of daily doses (mg/day) received
- Average of dosing frequency (day) per week
- Total amount of study drug (mg) received
- Total duration of treatment in number of months, calculated by last dosing day minus first dosing day add 1 then divided by 30.
- Number of patients who had duration in different categories: less than 12 months, between 12 months and 24 months, between 24 months and 36 months, between 36 months and 48 months, longer than 48 months.
- Number of patients which had average daily dose in different categories: <20 mg/day, ≥20 mg/day to <40 mg/day, ≥40 mg/day to <60 mg/day, ≥60 mg/day.

When calculating the total exposure duration on study drug, any dose interruption longer than 28 days will be excluded from the calculation.

	SAP PAL-003 Amendment 1 version 1.0	Page 21
---	-------------------------------------	---------

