14 SAFETY EVALUATIONS

Safety will be assessed by examining the incidence, exposure adjusted event rate, severity grade, and relationship to study drug of all treatment-emergent adverse events (TEAEs) reported during the study period. In addition, changes in clinical laboratory results and vital signs from baseline values from parent studies (PAL-002, PAL-004, 165-205) will be assessed. All safety data collected 30 days after the last dose will not be included in the analysis.

AEs will be coded in accordance with the MedDRA version 18.0. Only treatment-emergent adverse events (TEAEs) occurring and reported during the study period will be included in the adverse event summaries. A TEAE is defined as any AE that newly appeared or worsened in severity following initiation of the study drug administration till 30 days after last dose of the phase 2 studies (PAL-002, PAL-004, 165-205, PAL-003). If the onset date of an AE is missing, the AE will be considered treatment-emergent.

If the onset date or end date of an adverse event is partial, the same imputation rules described in section 10 will be applied:

The incidence and frequency of all treatment-emergent AEs will be summarized by SOC, preferred term (PT), and severity grade. For those AEs that occurred more than once during the study, the maximum severity will be used to summarize the AEs by severity. The SOCs and PTs will be displayed by descending order based on total population.

The treatment-emergent AEs will be summarized in the following categories:

- All AEs by SOC and preferred term
- All AEs by SOC, preferred term, and severity
- AEs assessed by the investigator as related to study drug by SOC and preferred term
- AEs assessed by the investigator as related by SOC, preferred term and severity
- Serious AEs (SAEs) by SOC and preferred term
- SAEs assessed by the investigator as possibly or probably related to study drug by SOC and preferred term
- All AEs by preferred term in descending frequency order
- Hypersensitivity AE by SOC and PT
- Hypersensitivity AE by SOC, PT and severity
- Neuropsychiatric AE by SOC, PT and severity

	SAP PAL-003 Amendment 1 version 1.0	Page 25
---	-------------------------------------	---------

AE assessed by investigators as related to PFS/Device malfunction

- AEs leading to dose interruption or reduction by SOC and preferred term
- AEs leading to withdrawal from study by SOC and preferred term

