- AEs leading to study drug discontinuation by SOC and preferred term
- Pregnancy
- Death

In addition to the standard summary tables and listings, the following information will also be summarized for AEs of special interest, and sponsor defined AEs of significance:

- Time to event onset from most recent dose for Anaphylaxis per NIAID/FAAN criteria and Anaphylaxis per NIAID/FAAN criteria meeting Brown's severe criteria
- Time to first event onset per subject from first dose
- Duration of the events
- Patient characteristics for subjects with special types of hypersensitivity AEs except for injection site reaction and arthralgia
- Actions related to study drug
- Common treatment
- Incidence rate over time

The AEs of special interest include:

- Anaphylaxis per NIAID/FAAN criteria
- Anaphylaxis per NIAID/FAAN criteria meeting Brown's severe criteria

The sponsor defined AEs of significance include:

- Hypersensitivity AEs
- Injection site reaction
- Generalized skin reaction with ≥ 14 day duration
- Injection site skin reaction with ≥ 14 day duration
- Arthralgia

The search strategy for AEs of special interest and sponsor defined AEs of significance is in [Appendix 1](#).

In addition to standard AE listings, by subject listings of injection site reaction AEs, AEs of special interest, sponsor defined AEs of significance, and psychiatric AEs under each

BIOMARIN	SAP PAL-003 Amendment 1 version 1.0	Page 26
-----------------	-------------------------------------	---------

identification strategies will be provided. Study drug dose level at onset date of each of the AE will be presented on the listings. AEs will be sorted by onset date, preferred term, and dose of study drug at event onset date. Number of Hypersensitivity AE will be plotted over time (1-6 month, 6-12 month, and once each year after).

Death information will also be displayed in a listing.

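### The hypersensitivity AE plot shows raw counts in bins that widen from about 6 to 12 months with no denominator, so a constant rate plots as a doubling at month 12

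*SAP*

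**What the plan says.** SAP Section 14 (Safety Evaluations) states: "Number of Hypersensitivity AE will be plotted over time (1-6 month, 6-12 month, and once each year after"). The quantity is a number of events. The sentence mentions no person-time, rate or number at risk.

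The same section plans two measures that could carry a denominator:

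- Its opening names exposure adjustment as a general safety measure: "Safety will be assessed by examining the incidence, exposure adjusted event rate, severity grade, and relationship to study drug".
- For AEs of special interest and sponsor-defined AEs of significance it lists "Incidence rate over time". Hypersensitivity AEs are first on the list of sponsor-defined AEs of significance, so this summary covers them.

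The SAP ties neither measure to the plot, and it gives neither a denominator nor time intervals for the second.

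Four other places show that the number of subjects under observation changes over time:

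- Section 4.1.2 defines the safety population as "all subjects who receive at least one dose of study drug throughout the study duration of any of the phase 2 studies".
- Section 3.3 restricts entry to PAL-003: "Only subjects who completed a previous pegvaliase study will be enrolled into this study".
- Section 4.6 says: "Subjects who discontinued prematurely will not be replaced".
- Section 11 sorts treatment duration into bands: "Number of patients who had duration in different categories: less than 12 months, between 12 months and 24 months", and so on up to "between 36 months and 48 months, longer than 48 months".

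**The concern.** A plot over time is read for one thing: whether events become more or less frequent as treatment continues. A raw count per bin is the event rate multiplied by the observation time in the bin. If that time differs between bins, the shape of the plot mixes risk with observation time.

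Two features of this plan make it differ. The bin width doubles at month 12, which pushes the year-2 bar up. Fewer subjects contribute to later bins, which pushes later bars down. The figure could therefore show a rise at one year followed by a decline when the rate never changed, or it could hide a real fall after the first year.

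Hypersensitivity AEs are the only AE type for which Section 14 names a plot over time, so a reader of the report may take the long-term pattern from this figure.

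**Working it through.** The SAP gives no event rate, dropout rate or sample size calculation, so there is no planned figure to reproduce. The check asks what the plot would show when the true rate is constant.

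**Step 1: bin width alone (SAP inputs only).** Expected count = rate × person-time. With a constant rate and no loss of subjects, person-time is proportional to bin width.

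- Year 2 against months 6 to 12: 12/6 = 2.00. The bar doubles.
- Rate fall that would plot as flat: 1 − 1/2.00 = 50%.
- A true 30% fall would plot as 0.70 × 2.00 = 1.40, a rise of 40%.
- First bin against months 6 to 12: 6/6 = 1.00 if the first bin starts at first dose, or 5/6 = 0.83 if months 1 to 6 are meant as elapsed months. The SAP does not say which. Month 6 is also named in both of the first two bins.

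**Step 2: adding loss of subjects (assumed inputs).** Let d be the yearly dropout share, with exponential dropout. Person-time from a to b years is then proportional to (1−d)^a − (1−d)^b. The values of d are assumptions, chosen to show a range.

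Year 2 against months 6 to 12, R = [(1−d) − (1−d)²] / [(1−d)^0.5 − (1−d)]:

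- d = 10%: 0.0900/0.0487 = 1.85
- d = 20%: 0.1600/0.0944 = 1.69
- d = 30%: 0.2100/0.1367 = 1.54

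Year 5 against year 2, both 12 months wide: (1−d)³. Year 5 is used because the top duration band in Section 11 is longer than 48 months.

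| Yearly dropout | Step at month 12, constant rate | Rate fall that plots as flat (1 − 1/R) | True 30% fall plots as (0.7 × R) | Year 5 / year 2, constant rate |
|---|---|---|---|---|
| 0% | 2.00 | 50% | 1.40 | 1.00 |
| 10% (assumed) | 1.85 | 46% | 1.29 | 0.729 (27% lower) |
| 20% (assumed) | 1.69 | 41% | 1.19 | 0.512 (49% lower) |
| 30% (assumed) | 1.54 | 35% | 1.08 | 0.343 (66% lower) |

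**Step 3: the same bins with a denominator.** Dividing each count by its own person-time returns the rate. Under a constant rate every bin then gives a ratio of 1.00, whatever the bin width or dropout.

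**Step 4: is a matching person-time already defined?** No. The only duration the SAP defines (Section 11) ends at the last dose and leaves out interruptions longer than 28 days. Treatment-emergent events (Section 14) are counted until 30 days after the last dose. Using the Section 11 duration as the denominator would put events in the numerator from time that is absent from the denominator.

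**The case against.** The strongest defence is that the trend is covered elsewhere. Section 14 plans an exposure adjusted event rate, an incidence rate over time for a group that includes hypersensitivity AEs, time to first event, and listings with onset dates. A count plot shows event burden, which is a fair display beside a rate. The bin labels would reveal the change in width, and numbers at risk may be left to figure shells that are not at hand.

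Much of this stands, and it limits the weight of the point. A reader might infer that the SAP has no exposure-adjusted look at hypersensitivity events. The document does not support that, because the two planned measures apply to them. The opposite inference, that those measures are sure to show the trend correctly, is not supported either: an incidence rate could mean events per person-time or percent of subjects with an event, and the SAP does not say which.

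What does not stand is that the missing denominator is mere detail. The sentence states what is plotted and in which bins, and that combination misleads across month 12. A sound table elsewhere does not correct the figure.

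It is also fair to object that every attrition figure rests on assumed dropout with a constant hazard, and that the model ignores the completers-only entry into PAL-003 and the dosing gaps between studies. A reader might take the 35% to 50% range of hidden falls, or the 27% to 66% decline, as estimates for this trial. They are not. Only the factor of 2 and the 50% follow from the SAP.

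**Conclusion.** The point holds for this one figure and is minor. From the SAP's own bins, with full follow-up, a constant rate plots as a 2-fold step up at month 12 and a true 50% fall plots as flat.

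The direction of the attrition effect follows from the document: dropouts are not replaced, only completers of a previous study continue, and durations run from under 12 to over 48 months. Its size does not follow; the 10% to 30% results only illustrate it.

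The constant rate is a benchmark for reading the plot, not an expectation stated in the SAP. The study is descriptive and no test or decision in the SAP uses the figure, so nothing beyond the reading of the figure is affected.

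**What to change.** Replace the plot sentence in Section 14 with wording such as:

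> Hypersensitivity AEs will be plotted as events per person-year in non-overlapping intervals (first dose to month 6, >6 to 12 months, >12 to 24 months, and yearly thereafter), with event counts, person-years and number of subjects at risk shown below the axis. Person-time runs over the same period in which TEAEs are counted (first dose in the parent study to 30 days after last dose). If interruptions longer than 28 days are removed from person-time, events with onset in them are removed from the numerator of this plot as well.

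Apply the same definition to "Incidence rate over time" so that the figure and the summary agree. Starting the first interval at first dose is an interpretation of the current bin label, which the sponsor should confirm.

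The cost is SAP wording and programming. No new data are needed, and no event leaves the tables or listings. Rates in late intervals with few person-years will be imprecise; the person-years below the axis make that visible.

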14.1 Immunogenicity

Immunogenicity testing will be performed using validated immunogenicity assays. Blood samples for routine immunogenicity testing will be collected prior to dosing as indicated in the protocol. Routine immunogenicity testing will include assays for anti-rAvPAL immunoglobulin G (IgG), anti-rAvPAL IgM, anti-PEG IgM, anti-PEG IgG, and neutralizing antibodies (NAb). In the event of a Hypersensitivity Reaction visit, sampling and testing will be performed for anti-rAvPAL-PEG IgE and anti-rAvPAL IgE as well as other potentially-related clinical laboratory tests, including CRP, C3/C4, and tryptase.

For immunogenicity analysis, an incidence table will be provided for PAL IgG, PAL IgM, PEG IgG, PEG IgM, and NAb. Titer summary statistics will also be provided for PAL IgG and PEG IgG, including mean, median, standard deviation, and minimum/maximum titer values at each study visit. The mean titers for PAL IgG and PEG IgG and percent positivity for PAL IgM, PEG IgM and NAb will be plotted over time. A listing of anti-rAvPAL-PEG IgE and anti-rAvPAL IgE test results will be provided by subject.

Anti-drug antibody impact on long-term safety will be evaluated. Plots and tables will be generated to explore the potential impact of anti-drug antibodies on hypersensitivity adverse event (HAE) frequency and severity. A listing will be provided of all hypersensitivity reaction visits with the most proximal antibody test result listed for each analyte, and when available, CRP, complement C3 and C4, and tryptase at the time of the event.

Anti-drug antibody impact on long-term efficacy will be evaluated. Plots and tables will be generated to explore the potential impact of anti-drug antibodies on blood Phe levels

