3.5 Sample Size Determination

Subject who participated in a previous pegvaliase study may be enrolled into this study. No formal sample size calculation was conducted.

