4 GENERAL ANALYSIS CONSIDERATION

Descriptive summaries of continuous variables will include the number of subjects (n), mean, standard deviation, median, minimum, and maximum. Descriptive summaries of categorical variables will include n and percent. Data from parent studies (PAL-002, PAL-004, 165-205) will be integrated together with data in PAL-003 for long term safety and efficacy analysis. The baseline value of an assessment is defined as the last available measurement prior to first administration of study drug from parent studies (PAL-002, PAL-004, 165-205), unless otherwise specified.

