8 DEMOGRAPHICS AND BASELINE CHARACTERISTICS

Subject characteristics and demographic information before the first dose of parent studies (PAL-002, PAL-004, 165-205) and the first dose of PAL-003 will be summarized. The demographics including age, age group (16 to <18 years of age, 18 to <66 years of age, \geq 66 years of age), gender, race and ethnicity will be summarized using descriptive statistics.

Subject characteristics will include height, weight, blood Phe concentration, intake of protein and dietary Phe, body mass index (BMI), BMI group ($<25 \text{ kg/m}^2$, $\geq 25 \text{ kg/m}^2$ and $<30 \text{ kg/m}^2$, $\geq 30 \text{ kg/m}^2$), and immunogenicity status (positive, negative, or titer value).

	SAP PAL-003 Amendment 1 version 1.0	Page 17
---	-------------------------------------	---------

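### PAL IgG and PEG IgG titers are plotted over time only as means, with no log scale or geometric mean named, so a few high titers can dominate the curve

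*SAP*

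**What the plan says.** SAP Section 14.1 asks for titer summary statistics for two analytes, PAL IgG and PEG IgG, "including mean, median, standard deviation, and minimum/maximum titer values at each study visit". For the time course it states: "The mean titers for PAL IgG and PEG IgG and percent positivity for PAL IgM, PEG IgM and NAb will be plotted over time". The IgG figure therefore shows the mean only. PAL IgM, PEG IgM and neutralizing antibody are shown as percent positive and are outside this point.

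The general rule in Section 4 has the same form: "Descriptive summaries of continuous variables will include the number of subjects (n), mean, standard deviation, median, minimum, and maximum". Neither section mentions a geometric mean, a log transformation or a log axis. The word arithmetic does not appear either, but a mean and standard deviation of titer values, with nothing further said, reads as untransformed.

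Three other places bear on the point:

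- Section 3.1 makes the immune response to long-term dosing a secondary objective.
- Section 4.5 has visit windows running to Week 416. Section 4.6 says that dropouts are not replaced and plans LOCF only for the primary objective.
- Section 8 lists negative as a possible baseline immunogenicity status. The SAP does not say what value a negative sample takes in a titer summary.

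**The concern.** Antibody titers are usually read from a dilution series, so their steps are multiplicative and their distribution tends to have a long right tail. An arithmetic mean of such data reflects the largest values more than the typical subject. The raw-scale SD often exceeds the mean, and then it describes spread poorly.

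This matters most for the figure. In a long extension the subjects who contribute change from visit to visit. If one or two subjects with very high titers leave, a raw mean can fall sharply although nobody still under observation has changed. A reader could take that for a waning immune response. The converse can happen when one subject's titer climbs. This is the only titer time-course figure that Section 14.1 specifies, and it serves a stated secondary objective.

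**Working it through.** The SAP has no titer value, titer spread or sample size to reproduce (Section 3.5: "No formal sample size calculation was conducted"). The figures below show scale only.

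**Assumptions, not from the SAP:** titers at a visit are log-normal with SD of ln(titer) s = 0.5, 1, 1.5 or 2; n = 40 subjects at the visit.

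**Formulas**

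- Arithmetic mean / geometric mean = exp(s²/2).
- Coefficient of variation (CV) of the arithmetic mean = √[(exp(s²) − 1)/n].
- CV of the geometric mean = √[exp(s²/n) − 1].

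Worked for s = 2: exp(2) = 7.39; √[(54.60 − 1)/40] = 1.16; √[exp(0.1) − 1] = 0.32.

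| s | Arithmetic / geometric mean | CV, arithmetic mean | CV, geometric mean |
|---|---|---|---|
| 0.5 | 1.13 | 8.4% | 7.9% |
| 1 | 1.65 | 21% | 16% |
| 1.5 | 3.08 | 46% | 24% |
| 2 | 7.39 | 116% | 32% |

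**Influence of the single highest subject** (simulation, n = 40, medians over samples)

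| s | Share of the total titer | Arithmetic mean if that subject leaves | Geometric mean if that subject leaves |
|---|---|---|---|
| 1 | 13% | −11% | −5% |
| 1.5 | 22% | −20% | −8% |
| 2 | 31% | −29% | −10% |

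**Raw-scale SD.** The population SD equals the mean when exp(s²) − 1 = 1, that is s = √(ln 2) = 0.83. In simulated samples of 40, the SD exceeds the mean in about 65% at s = 1 and 99% or more at s = 1.5 and 2, but almost never at s = 0.5.

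**A dropout example with invented titers.** Take 47 subjects at 1,000 and 3 at 100,000.

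- Arithmetic mean = (47,000 + 300,000)/50 = 6,940. The three high subjects supply 300,000/347,000 = 86% of it.
- Geometric mean = 1,000 × 100^(3/50) = 1,318. Median = 1,000.

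Now two of the three high-titer subjects leave and nobody else changes.

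- Arithmetic mean = (47,000 + 100,000)/48 = 3,063, a fall of 56%.
- Geometric mean = 1,000 × 100^(1/48) = 1,101, a fall of about 17%.
- Median is still 1,000.

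The geometric mean still moves, but far less.

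**The case against.** The strongest reply is that the table already holds what is needed. The same sentence that asks for the mean also asks for the median, minimum and maximum at every visit, so a reader can see the typical titer and detect skew from one row. That is correct, and it limits the point. It would be wrong to say that titers are summarised only by mean and SD. It does not help the figure, which shows the mean alone.

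Second, a reader might infer that a few subjects will drive the curve. The SAP does not support that. It reports no titer distribution, and at ln-SD 0.5 the choice of mean hardly matters. The fault is a risk created by the chosen statistic, not a demonstrated distortion. Nor does the SAP say that SDs will be plotted.

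Third, a reader might infer that geometric means remove the problem. They do not. A tenfold rise in one subject still multiplies the geometric mean by 10^(1/40) = 1.06 at n = 40, and dropout shifts it too. It also needs a value for negative samples, and where many samples are negative it depends on that choice. This objection stands in part. However, a raw mean needs the same value, so the gap exists already. Plotting the median avoids the choice as long as fewer than half the samples are negative.

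Fourth, a reader might extend the fault to the analyses of antibodies against hypersensitivity events and blood Phe. Section 14.1 says only that "Plots and tables will be generated to explore the potential impact of anti-drug antibodies on blood Phe levels", with similar wording for hypersensitivity. It names no titer scale for either, so nothing shows that they rest on the raw mean.

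Finally, mean, SD, median and range is the SAP's general rule for continuous variables, and Section 14.1 contradicts nothing. True: the point is a poor choice of statistic, not an inconsistency.

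**Conclusion.** The point holds as a modest, cheap improvement that the sponsor should make. On its natural reading, the SAP's titer time-course figure uses a raw-scale mean, which is sensitive to a few high values and to who remains under observation. The tabulated median softens this in the table but not in the figure.

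The size depends on skewness that the SAP does not report. Under the log-normal assumption the effect is negligible at ln-SD 0.5 and material from about 1 upward. The CVs also assume 40 subjects at a visit. Two analytes in a descriptive analysis are affected, and no hypothesis test or primary endpoint depends on it. If the sponsor already intends geometric means, the text still has to say so.

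**What to change.** In SAP Section 14.1:

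1. **Figure.** Plot PAL IgG and PEG IgG as geometric mean titers with 95% CI on a log axis. Medians with quartiles on a log axis are an acceptable alternative; the median is already tabulated.
2. **Table.** Replace the raw mean and SD by the geometric mean with 95% CI or geometric SD, computed on log titers. Keep the median, minimum and maximum.
3. **Negative samples.** State the value they are given, for example half the minimum required dilution.

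The cost is a few lines of SAP text and one changed statistic in outputs that are already planned. The one added decision is the value for negative samples. No new data are needed.
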